7.2.3 Unanticipated Serious Adverse Device Effect (USADE)

Serious adverse device effect which by its nature, incidence severity or outcome has not been identified in the current version of the risk analysis report.

NOTE: Anticipated: an effect which by its nature, incidence, severity or outcome has been previously identified in the risk analysis report

7.3 Adverse Event Reporting

All adverse events will be recorded on the adverse events page of the CRF.

Severity and relationship to study device will be assigned by the investigator as described in the section above.

Adverse events will be recorded after the subject (or delegate) has signed the informed consent and throughout the study including the follow-up termination visit. Adverse events should be reviewed and updated at each subsequent visit and during any phone contact with the subject.

Date issued:
05 Dec2018

SUBJECT: Functionality and Accuracy of the smART System in Real-Life ICU Settings

Number: CLT3_SY_P001 Revision 08

Page 28 of 38

Any SAE, whether deemed device-related or not, must be reported to the site Ethics Committee and to the sponsor's Safety Medical Officer by telephone and by Fax, as soon as possible after the investigator has become aware of its occurrence even if not all the information is available at the time of initial contact:

Safety Medical Officer contact information:

[name]

[contact]

Email: [contact]

The investigator must complete a SAE Form, and send it, via fax, to the Sponsor within 24 hours of becoming aware of the event. Accompanying documentation, such as copies of hospital case reports, autopsy report, and other documents when applicable, should be sent as soon as they are available.

The site's Ethics Committee must also be duly notified and dealt with, according to the local and federal regulations.

Subjects who have had an SAE must be followed clinically until all parameters (including laboratory) either have returned to normal or are stabilized.

8 Monitoring Plan

[figure not shown]
Monitoring functions shall be performed in compliance with Good Clinical Practices, EN ISO 14155:2011, as outlined in 21CFR§821.43(d) and 21CFR§812.46, and according to any other local regulations.

ART Healthcare will appoint a Clinical Monitor for this study. The Clinical Monitor should be qualified by training and experience to oversee the conduct of the study. The Clinical Monitor's responsibilities include maintaining regular contact with the investigational site, through telephone contact and on-site visits, to ensure that: 1) the study protocol is followed; 2) that complete, timely, and accurate data are gathered; 3) that problems with inconsistent and incomplete data are addressed; and 4) that complications and Unanticipated Adverse Device Effects are reported to the Sponsor.

9 Statistical considerations

9.1 Sample Size

The purpose of this study is to validate the functionality and accuracy of the smART System in real-life ICU settings by field study design. Therefore, descriptive statistics will be used to evaluate

the results. The proposed sample size of 20 subjects is sufficient to assess the performance of the smART™ Feeding Tube for the criteria presented in the primary endpoint. It should be noted that this figure does not include margin of dropout cases (not related to the device) which is normally estimated to be up to 10%.

9.2 Statistical Analysis

The analyses will be carried out according to intention to treat as well as per protocol. Categorical parameters will be summarized by frequencies and percentage, while quantitative variables will be summarized by mean, median, standard deviation and range. In particular, the following tests according to the parameter type will be performed:

- Continuous parameters will be presented by the estimated value and calculation of 95% confidence intervals.
- Nominal categorical parameters will be analyzed by Fisher exact test/ chi-square tests (in case of low observed frequencies).
- Ordinal categorical parameters will be analyzed by Wilcoxon rank sum test.

[figure not shown]
Alternatively, if data will support the assumption of normality:

- Comparison between continuous parameters will be analyzed by the appropriate Student T-test.

10 Data Management

Data from each subject will be recorded by the hospital (as needed and according to hospital procedures) and will transmitted manually to CRFs supplied by the sponsor. Quality check for errors and omissions will be performed to ensure the accuracy of the entered data. Information to be transmitted from the hospital source to the company CRF includes (but is not limited to): patient position changes, patient feedings, GRV (gastric residual volume), vital signs and medication record, etc.

The source data should be completed during the study by qualified personnel. All data must be filled out using ball pens (not pencils), accurately and promptly following each relevant step of the study. The CRF should be completed in full, i.e., no fields should be left blank once the subject has completed the study. CRFs entries corrections must be made only by lining out (single line) incorrect data and writing in the revisions. All corrections must be initialed and dated by the individual performing/recording the correction on the day of correction. If the reason for the change is not obvious, an explanation for the change should be recorded and attached to the CRF. Blacking out or using correction fluid or an eraser is not allowed to correct or eliminate data. The investigator

SUBJECT: Functionality and Accuracy of the smART System in Real-Life ICU Settings

Number: CLT3_SY_P001

Revision 08

Page 30 of 38

must review the CRFs for completeness and accuracy and must sign/date the forms where indicated. Signature stamps or substitutes are not acceptable.

The investigator will retain originals of CRFs, subject consent forms, and study data as permanent records for a period of 2 years or until the data is no longer required for regulatory purposes (the longest between these two).

Each set of CRFs should be reviewed by the sponsor's appointed monitor for accuracy and completion (signatures, dates, adverse events, serious adverse events, protocol deviations).

Using the software auxiliary tables, the following steps will be performed to protect patient privacy and to identify the user who collects the data:

- Define user and password for each nurse that will be authorized access nurse form tab.
- When exporting the CRF table to PDF (for signing purpose), each user that filled the data will have to sign.
- The system properties tab will be password protected and will be access only by ART-Healthcare's staff.

11 Amendments to the Protocol

No alterations or changes to this protocol will be permitted. However, should there be question or consideration of deviation from the protocol, clarification and approval must be sought from the sponsor.

Protocol modifications must be confirmed in writing prior to implementation.

12 Deviations from Study Plan

All major protocol amendments must be approved by the local IRB prior to implementation.

No protocol amendments should be adopted without prior written approval from the IRB except in the following cases:

- In order to eliminate immediate hazard to the subjects
- Changes involving only logistical or administrative aspects of the trial.

The investigator should document and explain any deviation from the approved protocol and to file waivers received from the sponsor, if applicable. Justification, and, if appropriate, the proposed protocol amendments should be submitted to:

1. The Sponsor for agreement
2. The IRB

SUBJECT: Functionality and Accuracy of the smART System in Real-Life ICU Settings

Number: CLT3_SY_P001

Revision 08

Page 31 of 38

Any subject treated in a manner that deviates from the protocol, or who is admitted into the study but is not eligible according to the protocol, may be ineligible for analysis and thereby compromises the study.

13 Device Accountability

ART Healthcare will provide the study site with the smART Systems for the duration of the study. The systems will be marked “for investigational use” and the investigator is responsible for storing the systems in a secure place to avoid unauthorized use.

Immediately upon completion of the study all systems and unused tubes will be return to ART Healthcare.

14 Statements of Compliance

This study will be conducted in compliance with the protocol after approval of the local Institutional Review Board (IRB) Committee, in accordance with the ethical principles that have their origin in the Declaration of Helsinki and in compliance with Good Clinical Practice (GCP) for medical devices per ISO 14155:2011, title 21 of the Code of Federal Regulations (21 CFR), part 812 (Investigational Device Exemptions), and the applicable regulatory requirements.

No deviation from the protocol, after sponsor's and Ethic Committee approval will be implemented without the prior review and approval except where it may be necessary to eliminate an immediate hazard to a research subject. In such case, the deviation will be reported to the Ethic Committee and the sponsor as soon as possible.

A copy of the protocol, Informed Consent Form (ICF) and advertising material must be submitted to the IRB. Written approval of the protocol, the Informed Consent Form and advertising material must be obtained prior to initiation of the study.

15 Informed Consent Process

Due to the sensitive nature of potential study subjects (e.g., unconscious, critically ill, etc.), independent physician and next of kin must sign informed consent prior to initiating any study related activities.

The Principal Investigator or his designee in accordance with institutional policy will obtain an Informed Consent, acceptable by the institution's IRB Committee. A written consent form bearing the full name of the subject and the signatures of the subject's delegate and an independent

		Date issued: 05 Dec2018
SUBJECT: Functionality and Accuracy of the smART System in Real-Life ICU Settings		
Number: CLT3_SY_P001	Revision 08	Page 32 of 38

physician will be obtained for each subject. The signed Informed Consent constitutes a confidential document and therefore should be archived in the Investigator File or in the Site's Record

The written Informed Consent form and any other written information to be provided to subject/delegate should be revised if any important new information becomes available that may be relevant to the subject's consent. Any revised written Informed Consent form, and written information must be approved by the IRB Committee before it is made available for re-signing. The subject's delegate should be informed in a timely manner if new information becomes available that may be relevant to the willingness of the delegate to keep the subject in the study. The communication of this information should be documented.

Neither the investigator, nor the trial staff, should coerce or unduly influence a subject/delegate to participate or to continue to participate in a trial.

The investigator, or a person designated by the investigator, should fully inform the subject/delegate of all pertinent aspects of the study including the approved written informed consent.

Before informed consent may be obtained, the investigator, or a person designated by the investigator, should provide the subject/delegate ample time and opportunity to inquire about details of the study and to decide whether or not to participate in the study. All questions about the study should be answered to the satisfaction of the subject.

Prior to a subject's enrollment into the study, the approved informed consent form should be signed and dated by the delegate, by an independent physician and by the person who is authorized to conduct the informed consent discussion.

16 Vulnerable Population

Most of the participants in this study will likely fall under the definition of "vulnerable population" (e.g., critically ill, unconscious, ventilated, etc.). Due to the sensitive nature of the study participants it is important to thoroughly explain the study to a delegate who is legally allowed to make medical decisions for the subject. Ample time should be given to the delegate to weigh and consider participation in the study. Patient/delegate is allowed to withdraw consent any time during the study. Informed consent signed by the patient (after gaining consciousness) may be obtained within reasonable time of up to two weeks from the end of the study (for the current patient).

17 Suspension or Premature Termination of the Study

The Sponsor reserves the right to discontinue the study at any time for any reason based on (but not exclusively) the following criteria:

- Technical problems in the smART device.

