4.1 Primary Endpoints

Functionality

- the system is able to accurately guide the user to ensure correct initial placement (verified by X-ray)
- the system is able to detect tube movement/displacement during ongoing use (verified by markings on the tube)
- the system automatically stops feeding when tube displacement is detected
- the system automatically stops feeding when reflux is detected
- the system automatically inflates the balloon when a reflux episode is detected

Safety

- occurrence of device related adverse events

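### Section 9.2 gives 95% confidence intervals only to continuous parameters, so the single-arm yes/no primary endpoints have no stated uncertainty, and section 9.1 gives no precision for 20 subjects

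*Combined protocol and SAP*

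**What the plan says.** Section 6.1 describes an open, prospective, single-arm study. Section 4.1 lists five functionality endpoints (correct initial placement, detection of displacement, and three automatic responses) and one safety endpoint, the occurrence of device-related adverse events. The three responses are each worded per detection. The response to displacement reads: "the system automatically stops feeding when tube displacement is detected". Two responses concern reflux. One is the feeding stop: "the system automatically stops feeding when reflux is detected". The other is the balloon: "the system automatically inflates the balloon when a reflux episode is detected".

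Section 9.2 sets the analysis by type of parameter:

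- For all categorical data: "Categorical parameters will be summarized by frequencies and percentage".
- For continuous data: "Continuous parameters will be presented by the estimated value and calculation of 95% confidence intervals".
- For nominal data: "Nominal categorical parameters will be analyzed by Fisher exact test/ chi-square tests (in case of low observed frequencies".
- For analysis sets: "The analyses will be carried out according to intention to treat as well as per protocol".

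Section 9.1 says the evaluation is descriptive and then states: "The proposed sample size of 20 subjects is sufficient to assess the performance of the smART™ Feeding Tube". It gives no expected rate, performance goal or interval width. It adds that the 20 leaves out a dropout margin of up to 10%.

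**The concern.** The only interval in the plan goes to a class of parameter that contains no primary endpoint. The tests assigned to the class that does contain them do not estimate a success rate, and section 9.2 names no groups for them to compare. Followed literally, the plan reports each primary result as a percentage with nothing to show how far the true rate could lie from it.

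Section 9.1 gives the study's purpose as validating functionality and accuracy. A perfect result from 20 patients, printed as 100%, could be taken as validation although it is compatible with a failure rate that matters. An interval also needs a denominator, and for the repeated displacement and reflux events the plan does not say whether that is patients or events.

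**Working it through.** **The plan's own figure.** The 20 can be neither reproduced nor refuted, because section 9.1 gives no rate, target or width from which to derive it. What can be calculated is the precision it provides.

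**Patient-level endpoints.** Inputs: n = 20 (section 9.1); n = 18 if the 10% dropout in section 9.1 occurs and is not replaced (20 × 0.90 = 18); 95% level (section 9.2). One yes/no result per subject is my assumption. The exact (Clopper-Pearson) lower limit for x = n is 0.025^(1/n), and the upper limit for x = 0 is 1 − 0.025^(1/n). Other cases use beta quantiles.

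| Result | Exact 95% limits |
|---|---|
| 20/20 | 0.025^(1/20) = 83.2% to 100% |
| 19/20 | 75.1% to 99.9% |
| 0/20 | 0% to 16.8% |
| 18/18 | 0.025^(1/18) = 81.5% to 100% |
| 0/18 | 0% to 18.5% |

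A device with a true success rate of 90% would still give 20/20 with probability 0.90^20 = 12%. An endpoint that arises in fewer patients has wider limits. With illustrative counts that are not in the documents, 10/10 has a lower limit of 69.2% and 5/5 one of 47.8%.

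**Endpoints worded per detection.** A patient may contribute no detections or many. Suppose 95 of 100 detections, 10 in each of 10 patients, are handled correctly (assumed). Treated as 100 independent events, the exact interval is 88.7% to 98.4%. With an intracluster correlation (ICC) of 0.3, the design effect is 1 + (10 − 1) × 0.3 = 3.7 and the effective number is 100/3.7 = 27.0. The interval then becomes 79.1% to 99.7%.

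A simulation shows when this matters. All its settings are assumed: 10 or 20 patients with detections, true success 90%, 95% or 98%, ICC 0.1 or 0.3, beta-binomial responses, 20,000 replicates per setting.

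| Detections per patient | Coverage of the pooled exact 95% interval |
|---|---|
| 1 to 3 | about 93% to 99% |
| 7 to 21 | about 62% to 92% |

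Pooling is therefore harmless if detections are rare and misleading if they are frequent. The documents give no event counts, so neither case can be preferred. A clustered interval has its own limit, since it cannot be formed when no response fails. With 98% success, 10 patients and 1 to 3 detections each, about 70% of replicates had no failure.

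**Displacement detection.** Under section 6.2.3, staff check the tube mark after the system alerts. The share of alerts confirmed this way is a positive predictive value, a term that appears in the list of abbreviations but not in the text provided. It says nothing about displacements with no alert. The same section plans a video recording for comparison with the console logs, and that could supply the missing denominator for movement visible at the face.

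**The case against.** The strongest reply is that section 9.1 declares a descriptive study with no hypothesis, so no power calculation is owed, and that anyone can compute patient-level limits from the reported frequencies. The first part stands: a reader might infer that 20 is too few, but with no performance goal in the documents there is nothing for it to fall short of. The second part holds for placement and adverse events. It does not hold for the repeated events, where the unit would be chosen after the data are seen.

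Three other tempting readings go too far.

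- *Replacement hides failed insertions.* Failed insertion is a withdrawal criterion (section 6.2.14) and early withdrawals may be replaced (section 6.2.12). But section 9.2 plans an intention-to-treat analysis and section 6.2.12 counts patients as enrolled from consent, so such patients are largely kept already. The placement denominator only needs to be stated.
- *Pooled intervals are badly wrong.* That requires frequent detections, which the documents do not establish.
- *Missed displacements cannot be found.* The planned video comparison may reveal them, and its detailed procedures are in a separate manual that is not among these documents.

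It is also fair to say that a one-sample chi-square test can compare a proportion with a reference value, and section 4.2 does plan one literature comparison. Such a test still gives no interval, and that comparison is a secondary endpoint.

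**Conclusion.** The point holds and should be fixed. As written, section 9.2 specifies no interval for any primary endpoint and assigns them tests that do not estimate a single-arm success rate, while section 9.1 asserts adequacy without stating precision. At patient level, a flawless 20/20 leaves a true failure rate of up to about 17% within the 95% limits, or about 18.5% with 18 evaluable subjects. These figures assume one result per subject. For the per-detection endpoints the effect of clustering ranges from negligible to large, depending on event counts the documents do not give. The finding concerns missing intervals, undefined denominators and an unsupported statement of adequacy. It does not show that 20 is the wrong number.

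**What to change.** The analysis rule is wrong as written, and these changes would correct it.

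1. In section 9.2, report exact (Clopper-Pearson) 95% intervals for correct initial placement and for the proportion of patients with at least one device-related adverse event. In line with the intention-to-treat analysis already planned, the placement denominator is every patient in whom insertion was attempted, including those later withdrawn and replaced. Show the per-protocol result beside it.
2. For the three endpoints worded per detection, report detections, correct responses and the number of patients contributing, overall and per patient. If patients contribute several detections, do not present a pooled binomial interval as though events were independent. Use an interval that allows for clustering by patient. Where failures are too few for that, give the exact interval for the proportion of patients with at least one detection in whom every response was correct. Show it beside the event counts, because that proportion falls as detections per patient rise.
3. For displacement detection, label the share of alerts confirmed by the tube mark as a positive predictive value. Claim sensitivity only from the video-to-log comparison planned in section 6.2.3.
4. Restrict Fisher, chi-square and rank-sum tests to secondary comparisons between groups, not the primary endpoints.
5. In section 9.1, replace the statement of adequacy with: *With 20 evaluable subjects, 20/20 gives an exact 95% lower limit of 83.2% and 0/20 an upper limit of 16.8% (81.5% and 18.5% with 18 evaluable); limits are wider for endpoints that arise in fewer patients.*

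The cost is a few lines of wording, modest extra analysis and a less favourable stated precision. No patients are added. Video review is needed only if sensitivity is to be claimed, and that comparison is already planned.

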4.2 Secondary Endpoints

- Ease of use of the system and the user interface by subjective questionnaire of staff
- Recording of impedance detected by the system and correlation to patient positioning
- Quantification of the amount of discarded nutritional supplement by implementing GRV test as needed and according to hospital procedures
- Reduction of aspiration of gastric contents percentage compared to standard feeding (as reported in literature).
- Correlation between patient clinical information and the occurrence of reflux and sensors data.

5 Study Conduct & Population

This study will be performed in accordance with the design and specific provisions of this protocol, in accordance with the ethical principles that have their origin in the Declaration of Helsinki, that are consistent with Good Clinical Practice (GCP), Title 21 of the Code of Federal Regulations (21 CFR), part 812 (Investigational Device Exemptions), and the applicable regulatory requirements.

SUBJECT: Functionality and Accuracy of the smART System in Real-Life ICU Settings

Number: CLT3_SY_P001

Revision 08

Page 17 of 38

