6.1 Type of Study

This is an open, prospective, single arm study in which the investigational device will be tested in real-life settings on patients admitted to the ICU who require enteral feeding.

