Every smART feeding tube removal should be documented in the CRF and the relevant device information (i.e., serial number) should be recorded. If a smART tube is replaced by a different smART tube, the reason for replacement should be documented and the serial number of the new device being used should be recorded.

- **Endoscopy/esophageal imaging**

One third of the study population will undergo endoscopy to evaluate potential trauma to the esophagus as a result of balloon inflation.

Endoscopy will be indicated for those patients who:

- Have been enrolled in the study for a duration of more than 5 days;

Or,

- Had noticeable blood residue on the feeding tube following tube removal.

PATIENT SAFETY THROUGH TECHNOLOGY

Date issued:
05 Dec2018

SUBJECT: Functionality and Accuracy of the smART System in Real-Life ICU Settings

Number: CLT3_SY_P001

Revision 08

Page 21 of 38

If by the time patient number 13 is enrolled, no endoscopies have been performed, the remaining 7 patients will undergo endoscopy for local evaluation of trauma in the area of the esophagus where the balloon is inflated.

Every effort will be made to obtain at least 7 patients with endoscopic assessment.

Procedure - Following tube removal (within 5 hrs.) patients eligible for endoscopy (based on the above definition) shall undergo an endoscopic procedure to evaluate the balloon inflation site. Specifically, any noticeable trauma to the esophagus shall be recorded in the relevant CRF pages (e.g., adverse event form).

- Aspiration of gastric contents recording

Local site procedure for tracheal suction should be followed as needed and according to hospital procedures. Once every eight hours a sample of at least 2 cc should be instilled in a LUKI trap. The sample should be appropriately labeled and recorded by the medical staff in the bed side CRF log (Pepsin Test). The sample should be kept frozen until transportation to the lab.

- Used/Unused Devices

Used devices will be returned back to the bag in which they were provided in by the sponsor. All the bags will be collected by the sponsor, and accountability logs will be updated accordingly.

All unused devices and study materials will be collected by the sponsor at the end of the study.

- Staff Questionnaires:

At the end of the study, staff will be required to complete a usability questionnaire assessing the ease of use and functionality of the device (refer to Appendix 2).

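### Section 9.2 assigns ordinal data a two-independent-sample rank-sum test in a one-arm study with no named groups, and names no method for repeated readings within a patient

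*Combined protocol and SAP*

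**What the plan says.** Section 6.1 gives the design: "This is an open, prospective, single arm study". Section 9.1 makes the evaluation descriptive ("Therefore, descriptive statistics will be used to evaluate"), and section 9.2 opens in the same vein: "Categorical parameters will be summarized by frequencies and percentage".

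Section 9.2 then commits to tests by parameter type. For ordinal data: "Ordinal categorical parameters will be analyzed by Wilcoxon rank sum test". Where normality is supported, it offers an alternative for continuous data: "Comparison between continuous parameters will be analyzed by the appropriate Student T-test". The only confidence intervals it mentions are for continuous parameters. It names no grouping variable and no one-sample, clustered or correlation method. It names no paired method either, unless the word for choosing the t-test is read to include one.

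The clearly ordinal endpoint is in section 4.2: "Ease of use of the system and the user interface by subjective questionnaire of staff". Section 6.2.3 sets the timing: "At the end of the study, staff will be required to complete a usability questionnaire assessing the ease of use and functionality of the device". Appendix 2 is the form: 13 items on 1-5 scales, with a field for the staff member's position.

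Section 4.2 also lists impedance in relation to patient positioning, and clinical information in relation to reflux and sensor data. Section 6.2.3 has repositioning recorded each time it happens and later correlated with reflux.

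**The concern.** A rank-sum test needs two independent samples. Here there is one arm, one device and one round of ratings. An analyst who follows section 9.2 literally must either leave out a prespecified test or find two groups after the data are in. The only split on the form is staff position, which no objective in section 3 or endpoint in section 4 asks about. With 13 items and no significance level stated, such a split invites unplanned p-values. The quantity of interest, how favourably staff rate the system and how precisely that is known, gets no interval.

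The second part concerns the repeated data. The positioning, impedance and reflux analyses use many readings from the same 20 patients, and section 9.2 offers nothing that accounts for this. The rank-sum test is its only rank-based method and the t-test is offered as the alternative under normality, so an analyst could take the rank-sum test as the fallback for non-normal readings. Pooling readings as if independent would then give the wrong error rate.

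**Working it through.** **No plan figure to reproduce.** The sample size of 20 comes without significance level, power, effect size or precision target, and section 9.2 gives no test level. Two-sided 5% is assumed below.

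**1. Can the named test run on the questionnaire?**
- Inputs: one arm (6.1); one completion at the end of the study (6.2.3); 1-5 scales (Appendix 2); no comparator rating.
- The rank-sum statistic is the sum of ranks of one group within the pooled sample. With the second group empty it is undefined, and standard software returns no statistic and no p-value.
- If two separate rater groups existed (12 and 8, assumed), the test would be valid: simulated type I error 0.044. So the obstacle is the missing second group.

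**2. What a precision statement would add.** The number of staff forms is not given. Taking 20 forms for illustration, 18 rating 4-5 is 90%, with exact (Clopper-Pearson) 95% CI 68% to 99%. Ten of 20 is 50%, with CI 27% to 73%. A bare percentage hides this width.

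**3. Rank-sum test on pooled repeated readings (conditional on the fallback reading).** Assumed, because the documents give none of it: m = 14 readings per patient, 20 patients, intraclass correlation (ICC) 0.2, 0.3 or 0.5, total SD 1, and a factor that is either fixed per patient (10 against 10) or balanced within patients (7 and 7).

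Hand approximation to the actual two-sided error:
- Factor within patients: the true standard error is √(1 − ICC) times the assumed one, so error ≈ 2[1 − Φ(1.96/√(1 − ICC))].
- Factor between patients: the variance is inflated by 1 + (m − 1)ICC, so error ≈ 2[1 − Φ(1.96/√(1 + 13·ICC))].

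| ICC | Within: approx. | Within: simulated | Between: approx. | Between: simulated |
|---|---|---|---|---|
| 0.2 | 1.96/√0.8 = 2.19 → 0.028 | 0.030 | 1.96/√3.6 = 1.03 → 0.30 | 0.299 |
| 0.3 | 1.96/√0.7 = 2.34 → 0.019 | 0.023 | 1.96/√4.9 = 0.89 → 0.38 | 0.382 |
| 0.5 | 1.96/√0.5 = 2.77 → 0.006 | 0.010 | 1.96/√7.5 = 0.72 → 0.47 | 0.482 |

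Simulated values use 2,000 studies per setting.

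**Power, factor within patients, shift 0.25 SD, ICC 0.5.** Each condition has 20 × 7 = 140 readings.
- Assumed standard error: √(2/140) = 0.120. True standard error: √(2 × 0.5/140) = 0.0845.
- Pooled test: it needs a difference of 1.96 × 0.120 = 0.234, so power ≈ Φ((0.25 − 0.234)/0.0845) = Φ(0.19) ≈ 0.57. Simulated rank-sum power is 0.55.
- One difference per patient: noncentrality 0.25/0.0845 = 2.96 on 19 degrees of freedom, so paired-t power ≈ 0.80. Simulated signed-rank power is 0.78.

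**4. Sensitivity to the assumptions.** With 5-level ordinal scores and 3 or 7 readings per patient (per condition for a within-patient factor), the error is 0.009 to 0.024 within patients (ICC 0.3 to 0.5) and 0.067 to 0.313 between patients (ICC 0.1 to 0.5). For 20 simple pairs with correlation 0.3, 0.5 and 0.7, the rank-sum error is 0.023, 0.010 and 0.002, while the signed-rank test stays at 0.044 to 0.053. A negative pair correlation of −0.3 would give 0.081. That is not the usual pattern for repeated readings on one patient.

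**The case against.** The strongest reply is that the plan is descriptive by its own account. Section 9.1 says so, and section 9.2 gives frequencies and percentages for categorical data, which covers the 5-point items. This stands. A reader might infer that the usability endpoint has no analysis that can be run. The documents do not support that: it has a descriptive one. What it lacks is a test that applies and a measure of precision. Nor does section 9.1 fully cure the wording, because section 9.2 goes on to commit to tests.

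The second reply is that the rank-sum line covers ordinal data only. Impedance is continuous, the positioning and reflux analyses are described as correlations, and no within-patient ordinal contrast is defined anywhere. This also stands, and it makes the error-rate figures conditional. What remains is that no method respecting repeated readings is named for these endpoints.

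A reader might also infer from the table a 30-48% false-positive rate for the planned contrasts. That does not follow. Those figures belong to a factor that differs between patients and depend on the assumed 14 readings. Position and reflux change within patients, and for a balanced within-patient factor the test is conservative. Where patients differ in how often each condition occurs, part of the contrast is between patients, and the result would lie between the two columns.

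Finally, staff position would give independent groups on which the rank-sum test is valid. True, but the plan does not name that comparison.

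**Conclusion.** The point holds in limited form. As written, the ordinal line of section 9.2 cannot be applied to the one clearly ordinal endpoint, because a single-arm study with one set of ratings supplies no second group. The remaining summary has no stated precision. This rests on the text alone.

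The repeated-readings part is an omission with a conditional consequence. If the rank-sum test were used on pooled readings, a factor balanced within patients would be tested at about 1-3% in place of 5%, with power of 55% against 78% in the example. Given positive correlation within patients, inflated false positives arise only to the extent that the factor differs between patients. These sizes rest on assumed correlations, readings per patient, balance and shift.

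Severity is low. Only secondary endpoints are involved, none has a hypothesis or success criterion, and no primary conclusion changes.

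**What to change.** In section 9.2, replace the rank-sum line with three statements:

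- (a) Each questionnaire item is reported as counts, median and percentage rating 4-5 with an exact 95% CI, using one form per staff member.
- (b) Any contrast or correlation that uses repeated readings is analysed with one summary or one difference per patient (signed-rank or paired t-test), or by a model with a patient random effect.
- (c) No two-sample test is run unless two independent groups are named in advance. If a comparison by staff position is wanted, it should be named here.

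The cost is a few lines of text. No new data are needed, and the questionnaire and sample size do not change.
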